6.4.2 Intravesical-BCG Dose Modification and Toxicity Management

6.4.2.1 Dose Modification

For patients enrolled in safety lead-in cohort, there will be no dose reduction for intravesical-BCG during induction treatment.

For patients enrolled in the safety lead-in cohort who do not have a DLT during induction treatment and for patients enrolled in dose expansion cohort, dose reduction is allowed for intravesical BCG at the treating physician's discretion in order to manage BCG-related toxicities ([Table 5](#)). For patients who are unable to tolerate full dose Intravesical BCG due to Intravesical BCG-related toxicities, dose reductions should be attempted before complete discontinuation of therapy. Initial reduction to -1 Level is suggested. Additional dose reductions to -2 Level dose can also be considered prior to complete discontinuation. If patient's symptoms improve during dose reduction, consider titrating dose back up to full dose.

Table 5 Intravesical BCG Dose levels for intra-patient dosing reduction

Full Dose	-1 Level	-2 Level
50 mg	33 mg	25 mg

Delayed Instillations

Delaying instillations of intravesical BCG is not encouraged but is allowed due to urinary tract infections, severe urinary symptoms, gross hematuria, traumatic catheterization or other circumstances at the discretion of the treating physician. Patients who postpone an instillation should resume treatment the following week. Dose and/or schedule modifications should be recorded on both source documents and CRFs.

Discontinuation of Instillations

Dose reduction should be considered before complete discontinuation of intravesical BCG instillations. Intravesical BCG should be discontinued for BCG treatment-related sepsis or extravesical (non-bladder) BCG infection.

Dwell Time

BCG administration and dwell time should follow local treatment protocols. Intravesical BCG dwell time may be up to 2 hours. Duration of retention of intravesical BCG can be shortened if medically indicated (e.g. pain or bladder spasm uncontrollable by symptomatic medications) at the treating physician's discretion as per usual standard of care. If needed, the use of an indwelling catheter during treatment, or anticholinergics, may be considered. If patient is unable to hold Intravesical BCG for 1 hour, a dose reduction should be applied.

Times of BCG Shortage

During periods of BCG shortage, split dose maintenance BCG therapy (1/2-1/3) according to institutional standard, may be used to maintain adequate BCG supply.

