8 EVALUATION CRITERIA

8.1 Safety Evaluation

Toxicity assessment is required prior to each BCG and/or avelumab treatment. Toxicity and grades will be classified using the NCI Common Terminology Criteria for Adverse Events (CTCAE) version 5.0. Dose limiting toxicity (DLT) will be monitored during the first 6 weeks of induction treatment with intravesical BCG and IV avelumab. Definition of DLT is described in [section 5.2.1](#).

Completion rate of induction therapy with combined BCG + avelumab is defined as completion of at least 5 of 6 treatments of each BCG and avelumab within 8 weeks during BCG induction phase.

Six-month treatment completion rate will be based on patients' completion of at least 2 of 3 BCG treatments within each 5 week period at the 6 Month maintenance treatment.

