10.2 Analytic Plan

Only evaluable patients as defined in Section 8.1.1 will be included in the statistical analysis. The proportion of patients receiving a complete induction course (at least 5 of 6 treatments of each BCG and avelumab within eight weeks of starting treatment) at 3 months and at 6 months will be calculated and a 95% Wilson score confidence interval constructed for the completion rate.

The 3-month and/or 6-month complete response (CR) rates will be summarized as the proportion (and 95% CI) of patients with complete tumor response at month 3 or 6 of study treatment.

Kaplan-Meier curves will be generated for overall survival, duration of response, progression-free survival, cystectomy-free survival, time to recurrence, and time to high-grade recurrence. Median survival time and 95% confidence intervals will be calculated. The EORTC QLQ-C30 questionnaire functional scales, symptom scales, and global health and quality of life scale will be summarized.

Frequency and severity of adverse events will be tabulated by body system, type and maximum grade. Serious adverse events will be listed.

Interim analysis

An interim safety analysis will be conducted when 3~6 patients have received ≥ 5 doses of BCG treatment in dose level 1. If the combination therapy in dose level 1 is not tolerated (2 or more patients experience a DLT), dose level -1 will be evaluated in additional 3~6 eligible patients. The decision rule is fully described in Section 5.2 Overall Study Design.

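### The induction completion rate pools patients barred from BCG dose reduction with patients allowed it, and no planned figure shows completion at the assigned BCG dose

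*Protocol*

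**What the plan says.** **Dosing rules.** For the safety lead-in, Protocol 6.4.2.1 states that "there will be no dose reduction for intravesical-BCG during induction treatment". It then says that "for patients enrolled in dose expansion cohort, dose reduction is allowed for intravesical BCG at the treating" physician's discretion, and does not confine this to maintenance. Table 5 gives the steps: 50 mg, then 33 mg, then 25 mg. For patients who cannot tolerate full dose, "dose reductions should be attempted before complete discontinuation of therapy"; if symptoms improve, the physician may "consider titrating dose back up to full dose". The dwell-time paragraph adds: "If patient is unable to hold Intravesical BCG for 1 hour, a dose reduction should be applied". That sentence names no cohort. On data capture, "Dose and/or schedule modifications should be recorded on both source documents and CRFs".

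**Endpoint and analysis.** Protocol 8.1 defines induction completion as "completion of at least 5 of 6 treatments of each BCG and avelumab within 8 weeks during BCG induction phase". Protocol 10.2 plans one figure with a Wilson 95% interval: "The proportion of patients receiving a complete induction course (at least 5 of 6 treatments of each BCG and avelumab within eight weeks" of starting. SAP 8a repeats it. Neither sets a BCG dose, and neither separates lead-in from expansion.

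**Population.** Protocol 10.2 uses the Section 8.1.1 set, meaning anyone given at least one dose of BCG and avelumab. SAP 5a defines a similar safety population for compliance and safety analyses. SAP 5c, however, assigns all of SAP Section 8, which contains the completion rate, to an evaluable set that mostly requires five induction doses.

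**The concern.** The same reaction to BCG can be scored differently in the two cohorts. A lead-in patient who cannot manage 50 mg has no reduction available during induction and may fall short of five instillations. An expansion patient with the same reaction may go to 33 or 25 mg, receive five instillations and count as a completer.

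This matters because the protocol treats dose as a question in its own right. Section 1.2 describes the lead-in as a check that full-dose BCG can be tolerated with avelumab, with reduced dosing to be studied if it cannot. Section 5.2 makes 33 mg a separate dose level with its own 3-6 patients. An expansion patient reduced to 33 mg receives the level -1 BCG dose but enters the result as a level 1 completer. With only the pooled rate in the report, a reader could take it as evidence for a BCG dose that some completers received for only part of induction.

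**Working it through.** **1. The plan's own precision figure.** Protocol 10.1 gives a Wilson lower bound of 37.6% for a 60% rate with 18 patients. The interval is

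[p + z²/(2n) ± z·√(p(1−p)/n + z²/(4n²))] / (1 + z²/n).

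With p = 0.60, n = 18 and z = 1.96 it runs from 37.6% to 78.9%, so the stated bound is reproduced. It refers to Month 6 completion; no expected rate or precision is given for induction.

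**2. Who falls under which rule.** Section 5.2 gives 3 lead-in plus 15 expansion patients, or 6 plus 12, for 18 at the final dose.
- Reduction permitted: 12/18 = 66.7% to 15/18 = 83.3%.
- Reduction barred in induction: 3/18 = 16.7% to 6/18 = 33.3%.

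The sentence permitting reduction also covers lead-in patients without a DLT during induction. Given the bar just before it, this is best read as applying after induction.

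The reductions available depend on the final dose: 33 or 25 mg if it is 50 mg, and only 25 mg if it is 33 mg.

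**3. When a reduction changes a patient's status.** Mirror the primary definition by requiring at least 5 of 6 instillations at the assigned dose.
- Six given, reduction starts at instillation s and is not reversed: s − 1 at the assigned dose. For s = 1 to 5 this is 0 to 4 (not met); for s = 6 it is 5 (met).
- Six given, one reduced and then full dose again: 5 (met).
- Five given, any reduction: at most 4 (not met).

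A reduced completer therefore lowers the assigned-dose rate by either 0 or 1/18 = 5.6 points.

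**4. Illustration.** The documents give no reduction frequency. Assume 15 completers among 18, three of whom had BCG reduced.

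| Assigned-dose status of the three | Rate | Wilson 95% CI |
|---|---|---|
| All meet the rule (one reduced of six) | 15/18 = 83.3% | 60.8-94.2 |
| None meets the rule | 12/18 = 66.7% | 43.7-83.7 |

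The planned analysis would show 83.3% in both rows.

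**5. Denominator.** Under Protocol 6.7 and 8.2.1, patients who stop early are replaced but stay in the 8.1.1 set, so n can exceed 18. Assume three replaced non-completers, giving n = 21. The any-dose rate is 15/21 = 71.4% (50.0-86.2), and the assigned-dose rate is at worst 12/21 = 57.1% (36.5-75.5). The largest step per patient is 1/21 = 4.8 points.

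Under SAP 5c most patients with fewer than five doses leave the denominator; the exception is doses missed because of treatment-related grade 3-4 events. A completion rate in that set is nearly 100% by construction and conflicts with Protocol 10.2.

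**6. What the lead-in shows alone.** Even full completion at the fixed dose is weak evidence: 3/3 has a Wilson interval of 43.9-100%, and 6/6 has 61.0-100%.

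**The case against.** The strongest reply is that the endpoint measures what it claims. Section 1.5.1 defines a full induction course by the number of instillations, and intolerance as failing to receive that number. Section 1.2 says BCG works in split dosing. No section calls the pooled rate tolerability of a fixed dose. A fixed-dose lead-in followed by expansion with ordinary dose management is a deliberate design, and the lead-in DLT rule is the test of full dose. The induction rate carries no null hypothesis, threshold or go/no-go rule.

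All of this stands, and it rules out several stronger readings. A reader might infer that the primary endpoint is invalid or biased; the documents do not support that, because any-dose completion is a legitimate quantity and is the one stated. A reader might infer that the 3+3 decision is contaminated; it is not, because reduction in induction is barred for the patients who drive it. A reader might infer that completion will be overstated by some known amount; the number of reduced patients appears nowhere and may be zero.

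The contrast between cohorts should not be drawn too sharply either. Lead-in patients may still have delays, shorter dwell and symptomatic treatment, and may miss one instillation, so intolerance of 50 mg need not mean failure. The dwell-time instruction is not limited to expansion.

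The objection does not supply the missing output. Dose changes go on the CRFs and SAP 5a mentions compliance, but no summary of dose received is defined. Most final-dose patients are treated under the permissive rule.

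**Conclusion.** The point holds as one of reporting and interpretation, limited to induction. The pooled rate is sound as completion with reductions permitted, but it combines two dosing rules, and nothing planned shows how many patients completed at the dose assigned to them.

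The effect is bounded per patient (0 to 5.6 points with n = 18, at most 4.8 with n = 21) but unknown in total. The illustrated gap of up to 16.7 points (83.3 − 66.7) rests entirely on the assumption of three reduced completers and is a worst case for that number. The conclusion also rests on reading the lead-in bar as covering all of induction and the expansion permission as including induction.

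The population mismatch between SAP 5c and Protocol 10.2 is a definite fault and does not depend on how many patients are reduced.

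**What to change.** 1. Keep the any-dose completion rate as primary and word the conclusion as tolerability with BCG reductions permitted.
2. Add to Protocol 10.2 and SAP 8a one descriptive supportive rate with a Wilson 95% CI: the proportion receiving, within 8 weeks, five or more of the six induction BCG instillations at the assigned dose (50 mg, or 33 mg if level -1 is final), together with the avelumab treatments that the primary definition requires. One reduced instillation out of six does not disqualify a patient.
3. Show separately for lead-in and expansion the number of completers and the number with any BCG reduction during induction.
4. State in SAP 8a that both rates use the at-least-one-dose set (Protocol 8.1.1, SAP 5a), not the SAP 5c evaluable set.

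The cost is one extra rate, a cohort split in one table, and edits to two documents. Dose modifications are already required on the CRFs, so no new data are needed and no maintenance-dose table is called for. The drawbacks are modest. The supportive rate can only equal or fall below the primary, and it will be imprecise. Its 5-of-6 threshold is a convention chosen to mirror the primary definition: it fails some patients who had the assigned dose for most of induction, such as one first reduced at instillation 5. The cohort counts in step 3 let the reader see past that cut-off.

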5.2 Overall Study Design

This is an open-label phase Ib trial of avelumab and intravesical BCG in patients with NMIBC. The study will utilize a modified 3+3 design for potential dose de-escalation in case of patients cannot tolerate to a full dose intravesical BCG. In order to adequately assess safety data at the conclusion of this combination therapy, 3~6 patients will be enrolled at starting dose level (dose level 1). Dose limiting toxicity will be based on the first 6 weeks of proposed study treatment. If 0/3 patients experience a DLT, dose expansion cohort will be activated for additional 15 patients. If 1/3 patients experiences a DLT, the dose level 1 will be expanded to 3 more patients. If 1/6 patients experiences a DLT, the dose expansion cohort will be activated for additional 12 patients. If 2 or more of the 6 patients experience a DLT, the dose level -1 will be evaluated.

At the dose level 1, 3~6 patients will be enrolled to evaluate the safety of proposed combination therapy with standard BCG dosing (50 mg) plus avelumab (10 mg/kg, IV weekly during BCG and every two weeks between BCG). The ability of patients to receive a complete induction course of combination therapy is defined as 5 of 6 weekly treatments of BCG with weekly infusion of avelumab within an 8 week period. Patients will continue maintenance therapy if they tolerate the induction course. Eligible patients will receive avelumab 10 mg/kg, IV weekly dosing plus intravesical BCG 50 mg weekly, 6 weeks on, then 6 weeks off during induction and will continue on a standard maintenance regimen with combination therapy for 1 year. Maintenance therapy beyond 1 year will be at the discretion of the treating physician and will be BCG monotherapy.

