5.2.1 Definition of Dose limiting toxicity

During safety lead-in phase, Dose limiting toxicity (DLT) will be monitored during the first 6 weeks of the combination avelumab and intravesical BCG. DLTs will be defined as any and all adverse events at least possibly related to study drug which occur in the DLT evaluation period and meet the criteria below, as evaluated by the NCI-CTCAE version 5.0.

Note: DLTs and other toxicities will be discussed between the Principal Investigator, and the Data Safety Monitoring Committee (DSMC). The discussions are the basis for the decisions regarding dose expansion (or de-escalation) according to the rules of the protocol.

DLT will be classified as either hematologic or non-hematologic toxicity (assessed in accordance with the CTCAE Version 5.0 criteria).

The following are DLTs:

1. Toxicity causing greater than 2 weeks of dose delay. For example, if a subject has dose delay greater than 2 weeks due to an AE, such AE is a DLT.
2. Grade 4 neutropenia greater than 5 days.
3. ALT/AST $> 3x$ ULN with bilirubin $> 2x$ ULN without another explanation (e.g., cholestasis)
4. Any Grade 3 hypersensitivity reaction is a DLT
5. Grade 4 thrombocytopenia of any duration
6. Grade 3 thrombocytopenia with significant hemorrhage of any duration
7. Febrile neutropenia

And, any non-hematological Grade ≥ 3 toxicities will be a DLT.

The following may be considered as exceptions to DLTs:

1. Grade 3 nausea, vomiting, or diarrhea and Grade 4 vomiting or diarrhea in the absence of maximal medical therapy that resolves in 72 hours
2. Grade 3 fatigue lasting < 5 days
3. Grade 3 hypertension that can be controlled with medical therapy
4. An increase of indirect (unconjugated) bilirubin indicative of Gilbert's syndrome
5. Serum lipase and/or serum amylase CTCAE Grade 3 ≤ 7 consecutive days without clinical signs or symptoms of pancreatitis

5.2.1.1 Definition of DLT Evaluable Population:

Patients enrolled in safety lead-in cohort who receive at least 4 doses and complete the DLT observation period (the first 42 days of induction treatment), unless the patient discontinued the study treatment due to a DLT.

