6.3.2 Intravesical BCG

During BCG Induction Course (12 weeks), patients will receive BCG at the assigned dose weekly for a total of six doses. During the BCG Maintenance Course, patients receive BCG at the assigned dose weekly for a total of three doses per cycle at Months 3, 6, and 12. Patients with persistent disease at the Month 3 cystoscopy can undergo an additional repeat induction course of BCG + avelumab, providing no disease progression. Primary outcome remains completion of maintenance at 6 Month from trial initiation.

Induction phase (cycle 1):

- Once weekly for up to six doses

Maintenance phase (Month 3, 6, and 12):

- Once weekly for 3 doses per cycle

Locally sourced commercial stock of BCG should be used. A single dose consists of one reconstituted vial. For intravesical use, the entire vial is reconstituted with sterile saline. BCG is viable upon reconstitution. Refer to the package insert for detailed preparation instructions and stability data. During times of BCG shortage, split dose maintenance therapy (1/2-1/3) will be permitted at PI discretion.

Patients should minimize fluid intake before treatment with BCG. Additionally, complete bladder drainage should occur via catheter drainage placed immediately prior to BCG administration. Premedication for BCG therapy to ensure adequate instillation is acceptable.

Instill BCG (intravesical) by gravity; retain for as long as possible, according to local treatment protocols. Following bladder instillation, patients should be instructed to void in a seated position in order to avoid the splashing of urine; burning may occur with the first void following therapy. Prior to flushing, disinfect the urine for 15 minutes with an equal amount of household bleach (this should be done for the first 6 hours after therapy). After administration, patients should drink plenty of water in order to flush the bladder.

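### Protocol 6.4.2.1 does not say whether the dwell-time dose reduction applies to lead-in patients in induction, and the DLT-evaluable definition would let a patient reduced below 50 mg count as DLT-free at dose level 1

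*Protocol*

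**What the plan says.** Protocol 6.4.2.1 begins with a rule for the lead-in: "For patients enrolled in safety lead-in cohort, there will be no dose reduction for intravesical-BCG during induction treatment". Its second paragraph allows discretionary reduction for expansion patients and for lead-in patients who had no DLT during induction. For the size of the step it says "Initial reduction to -1 Level is suggested"; Table 5 sets that level at 33 mg and the next at 25 mg.

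Under Dwell Time, the same section says "Duration of retention of intravesical BCG can be shortened if medically indicated", at the treating physician's discretion, and then "If patient is unable to hold Intravesical BCG for 1 hour, a dose reduction should be applied". Neither sentence is limited to a cohort or phase, and neither refers back to the opening rule.

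Protocol 5.2 sets out what dose level 1 tests: "3~6 patients will be enrolled to evaluate the safety of proposed combination therapy with standard BCG dosing (50 mg") plus avelumab. Dose level -1 uses BCG 33 mg. The DLT window is weeks 1 to 6.

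Protocol 5.2.1.1 defines the DLT-evaluable set as "Patients enrolled in safety lead-in cohort who receive at least 4 doses and complete the DLT observation period", with an exception for patients who stopped because of a DLT. SAP 7.a.ii repeats it. Neither requires the doses to be at the assigned level. The SAP is silent on dwell time and on BCG reduction.

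**The concern.** The lead-in exists to learn whether full-dose BCG with weekly avelumab can be tolerated. Its decision rests on three to six patients, so each one is a third to a sixth of the evidence. A patient whose bladder cannot hold the instillation is informative about tolerance of 50 mg. If that patient is reduced, finishes the window without a DLT and is then counted as DLT-free at 50 mg, the count favours expansion on the strength of exposure that was partly at a lower dose. The suggested first reduction is to 33 mg, the BCG dose of level -1, so the two dose levels would be partly mixed in the comparison the design depends on. A further 12 to 15 patients would then be enrolled at level 1.

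**Working it through.** No figure in the documents is at issue, so the main check sets the texts side by side.

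| Question | What the text gives |
|---|---|
| May a lead-in patient be reduced during induction? | Opening of 6.4.2.1: no |
| What if a patient cannot hold BCG for 1 hour? | Dwell Time, 6.4.2.1: reduce; no cohort or phase named |
| Which sentence prevails? | Not stated |
| Is failing the 1-hour hold a DLT? | Not listed in 5.2.1 |
| Does DLT evaluability require the assigned dose? | No: at least 4 doses and 42 days |
| Does induction completion require the assigned dose? | No: 5 of 6 treatments of each agent (8.1) |

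**Route to a miscount.** Suppose a level 1 patient has bladder symptoms below Grade 3, with no delay beyond 2 weeks, but cannot hold for 1 hour. Nothing in 5.2.1 makes this a DLT. If the dwell sentence is followed, later instillations are given at 33 mg. The patient still has at least 4 doses and 42 days, so is evaluable and DLT-free. With two other DLT-free patients the result is 0/3, and 15 more are enrolled at 50 mg, although only two patients took that dose throughout. The same route exists in a level -1 lead-in, where a reduced patient would receive less than 33 mg.

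**Chance of at least one patient failing the hold.** The documents give no rate. If the rate is f per patient, the chance in n patients is 1 − (1 − f)^n.
- f = 10% (assumed): 1 − 0.9³ = 0.271; 1 − 0.9⁶ = 0.469.
- f = 20% (assumed): 1 − 0.8³ = 0.488; 1 − 0.8⁶ = 0.738.

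These are chances that such a patient exists, not chances that the decision changes.

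**Effect on the decision, illustration only.** Under the 5.2 rule (expand on 0/3, or on 1/3 followed by 0/3), with DLT rate p:

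P(expand) = (1 − p)³ + 3p(1 − p)² × (1 − p)³

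With everyone at 50 mg:
- p = 0.30: 0.343 + 0.441 × 0.343 = 0.494.
- p = 0.40: 0.216 + 0.432 × 0.216 = 0.309.

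Let a share q of patients be reduced and their DLT risk become r × p. The effective rate is p(1 − q) + q × r × p. For p = 0.40, q = 0.20 and r = 0.5 it is 0.32 + 0.04 = 0.36, and P(expand) = 0.262 + 0.442 × 0.262 = 0.378.

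Over q from 10% to 50% and r from 0.25 to 0.75:
- true rate 40%: 0.326 to 0.600, against 0.309;
- true rate 30%: 0.510 to 0.736, against 0.494.

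If reduction does not change the DLT risk (r = 1), or no lead-in patient is reduced (q = 0), the probability does not move. All of p, q and r are assumptions.

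**The case against.** The best reply is that there is no real conflict. The opening rule names a cohort and a phase, while Dwell Time is general management text for all patients and cycles, and a specific rule ordinarily limits a general one. This has force. A reader might infer that 6.4.2.1 contains two unconditional commands of equal weight; it does not, because the bar is conditional on cohort and phase and the dwell sentence says should, not must. What remains is that the protocol never states this precedence, and the dwell sentence is more directive than the discretionary wording before it.

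The second reply is that safeguards exist. Under 5.2.1, DLTs and other toxicities are discussed between the Principal Investigator and the DSMC as the basis for expanding or de-escalating. Section 6.4.2.1 has dose changes recorded in source documents and CRFs. A related non-haematological toxicity of Grade 3 or more is a DLT, and none of the listed exceptions is a bladder symptom. These make a reduced patient visible and capture severe intolerance. They do not tell the committee how to count a reduced patient, because it decides under the protocol's rules and no rule covers that case.

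The third reply concerns size. A reader might take the irritable bladder (about 60%) and urgency (6% to 50%) figures in 1.2.1 as a guide to how many would fail the hold. They are rates of any occurrence. Table 6 describes such symptoms as expected and usually gone within 48 hours, and 6.4.2.1 mentions a catheter or anticholinergics. This objection stands: those figures do not support a failure rate.

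Nor does Protocol 6.3.2 settle the matter. Its instruction to "retain for as long as possible, according to local treatment protocols" says nothing about dose or evaluability.

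**Conclusion.** The drafting conflict is real, and the evaluability definition does not catch its consequence. If the dwell rule is followed for a lead-in patient in induction, that patient could be counted as DLT-free at a dose not received throughout. If the bar governs, the same miscount can arise only through a deviation, since the definition would still admit the patient.

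The documents do not support the stronger inference that the 3+3 decision is compromised, or that 50 mg would probably be cleared wrongly. A changed decision needs a patient who fails the hold, a site that follows the dwell sentence, a reduction that prevents a DLT 50 mg would have caused, and a cohort in which that one DLT tips the rule. None of these has a probability in the documents. The direction is clear if a lower dose lowers DLT risk: towards expansion. The size cannot be derived. The point merits a correction because the decision rests on so few patients and the remedy is small.

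**What to change.** 1. In Protocol 6.4.2.1, reconcile the opening sentence and the Dwell Time sentence for lead-in patients during induction, with an explicit exception or cross-reference. Which clinical rule applies is for the sponsor.
2. In Protocol 5.2.1.1 and SAP 7.a.ii, state that a lead-in patient who received BCG below the assigned level in the 42-day window, by rule or by deviation, is flagged and not counted as DLT-free at that level, while any DLT in that patient still counts.

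The second change is useful whichever rule is kept. It is one reasonable convention rather than one the documents compel, and it is deliberately asymmetric: it leans towards caution, because reduced patients can add DLTs but not DLT-free results.

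The cost is one clarifying sentence in 6.4.2.1, one sentence in each evaluability definition, and possibly one lead-in patient replaced. No new data are needed, since dose changes are already recorded on the CRFs.
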